4.2 Secondary Endpoints

The following is a list of other secondary endpoints to be explored:

- 1. Completeness, in percentage, of resection based on endoscopy film and/or photographs in addition to diagnostic assessment of specimen by the independent pathologist.
- 2. Presence of colon stenosis based on endoscopy film and/or photographs.
- 3. Rate of persistence of disease at the location of resection at 90 days.
- 4. Histologic assessment of the diagnostic value of the collected specimens.

4.3 Inclusion Criteria

Subjects are required to meet **ALL** the following inclusion criteria in order to be included in this clinical study:

- 1. Subjects aged \geq 18 to \leq 85 years.
- 2. At least one recurrent flat or sessile colorectal lesion up to 6 cm in diameter and/or length.
- 3. Presence of lesion where the EndoRotor® may be used to resect recurrent neoplasia.
- 4. Favorable anatomy that allows the investigator to access the lesion.
- 5. Subject is able and willing to comply with site standard medical follow-up, including a 90-day follow-up visit.
- 6. Subject has been informed of the nature of the study, agrees to participate and has signed the consent form

4.4 Exclusion Criteria

Subjects are required to meet **NONE** of the following exclusion criteria to be included in this clinical study:

- 1. Inability to give informed consent.
- 2. Subject age is <18 or >85 years of age.
- 3. Presence of a lesion that represents cancer or has a high chance of harboring submucosal invasive cancer.
- 4. Presence of synchronous lesions intended for resection that would necessitate use of a concomitant resection modality
- 5. Medical reasons the procedure cannot be performed (i.e. labile blood pressure, anticoagulation laboratory levels that are too high and risk excessive bleeding, systemic infection etc.)
- 6. Active antiplatelet therapy (Plavix®, 325mg aspirin therapy, etc.) where subject cannot be off treatment for at least 1 week prior to index procedure.
- 7. Inability to undergo a procedure under Propofol sedation or general anesthesia.
- 8. Female patients known to be pregnant.
- 9. Co-morbid conditions that, in the opinion of the investigator, place the subject at an unacceptable surgical risk (e.g., severe chronic obstructive pulmonary disease, hepatic failure, cardiac disease, autoimmune disorders or conditions of severe immunosuppression).
- 10. Any clinical evidence that the investigator feels would place the subject at increased risk with the deployment of the device.
- 11. Subject is participating in another study of a device, medication, biologic, or other agent within 30 days of enrollment and could, in the opinion of the investigator, impact the results of this study.
- 12. Subject has other medical, social or psychological problems that in the opinion of the investigator would preclude them from receiving this treatment and the procedures and participating in evaluations pre- and post-treatment.

5.0 STUDY PROCEDURES

5.1 Subject Screening

All subjects presenting to the institution who are scheduled to undergo flexible interventional colonoscopy for colon polyps will be informed of the study and offered enrollment if they meet the inclusion/exclusion criteria.

A member of the study team shall perform a preliminary evaluation of the potential participant's medical history and previously performed examinations to assess for initial eligibility. If the subject is willing to participate in the study, a written consent will be obtained. All subjects that have consented to participate in the study will be entered into the Enrollment / Screening Log.

Any subject that fails the screening process after providing consent will be considered a screen failure; the reason for failing the screen will be recorded on the log.

5.2 Informed Consent

Written Informed Consent, with the IRB approved consent form, will be obtained for all subjects **prior** to any data collection for the study in accordance with 21 CFR 50.20. The subject shall be given adequate time to read the informed consent form and will have the study process explained to them prior to signing the Informed Consent document. All subjects are to receive copies of their signed informed consent documentation.

5.3 Subject Enrollment and Withdrawal

All subjects requiring interventional colonoscopy for colon polyps are potential study candidates and will be screened for eligibility. Every effort will be made to ensure eligibility of the participants prior to study procedure. Actual enrollment in the study occurs at the time of informed consent.

Subjects who do not meet all inclusion / exclusion criteria (e.g., including inability to reach the target area or colon anatomy not conducive to tissue resection) will be considered a screen failure and will not be followed in the study (no data will be collected on these subjects). Subjects in whom the Interscope EndoRotor® is inserted into the colon and resection is attempted, but the procedure is aborted without resection of tissue, will be followed through discharge for safety. At discharge, the subject will be assessed for safety only and the subject will be allowed to exit the study.

Subjects may withdraw at any time from the clinical study without jeopardy or prejudice. If a subject prematurely terminates from the study, the reason for study termination will be recorded and the results will be tabulated by number and percent for each category. If termination is the result of an adverse event or death, an Adverse Event Form will also be completed. Subjects who withdraw consent after treatment will have their data evaluated until the time of their withdrawal

The Investigator should follow all unresolved serious adverse events until the events are resolved, the subject is lost to follow-up, the subject has withdrawn consent, or the adverse event is otherwise explained.

All reasonable efforts will be made to obtain complete data for all subjects; however, missing medical observations will occur due to loss to follow-up, withdrawal, or non-adherence with required assessments. If a subject cannot be located, they will be considered lost to follow-up. If they are contacted but refuse to return for visits or they actively request to withdraw from the study, they will be considered withdrawals. Data collected up to the time of lost to follow-up, and withdrawal of consent will be maintained in the study database and used for analysis purposes, as appropriate. These subjects will not be replaced.

Subjects who are enrolled and treated, but who are later discovered to not meet all of the study eligibility criteria will remain in the study and follow-up data will be collected. A protocol deviation will be completed for study subjects who are found to be ineligible after enrollment.

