5.6 Baseline Evaluation, not greater than 14 days prior to the Index Procedure

Baseline data will be collected after the subject signs the informed consent form in order to confirm **all** inclusion and **no** exclusion criteria are met. All assessments must be completed within the 14 days prior to undergoing the study procedure, with the exception of the pregnancy test. A negative pregnancy test within 1 day before the study procedure is required for women of childbearing potential.

The following baseline evaluations will be assessed and recorded on all patients who provide written informed consent:

- Demographic information
- Medical and surgical history, including risk factors
- Pregnancy test results (completed within 1 day before the study procedure)
- Physical examination
 - Vital signs
 - Height and weight
 - o Target review of symptoms
- Assessment against I/E criteria

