8.1 Population Demographics

The demographics and medical history will be presented in tabular form for all subjects enrolled in this study. Means, standard deviations, and Ns will be used to summarize continuous characteristics such as age. Percentages and counts of subjects exhibiting a characteristic will be used to summarize categorical characteristics such as gender.

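### Section 5.3 sets no cut-off for calling a subject a screen failure, so a failure to position the EndoRotor can be classed as ineligibility and appear in no analysis set

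*Combined protocol and SAP*

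**What the plan says.** Section 5.3 fixes enrollment early: "Actual enrollment in the study occurs at the time of informed consent". The same section then lists access and anatomy among the grounds for removal: "inability to reach the target area or colon anatomy not conducive to tissue resection) will be considered a screen failure". Such subjects "will not be followed in the study (no data will be collected on these subjects". No time limit is attached. The criterion behind the rule, inclusion 4 in section 4.3, has none either: "Favorable anatomy that allows the investigator to access the lesion".

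The next sentence of 5.3 treats one group differently. If the device was inserted and resection was attempted but no tissue came away, the subject is followed for safety to discharge and then exits. Section 5.3 also keeps in the study any subject who was treated and later found ineligible.

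Other sections require data on subjects who fail after consent. Section 5.1: "the reason for failing the screen will be recorded on the log". Section 5.6: "The following baseline evaluations will be assessed and recorded on all patients who provide written informed consent". Section 8.1 wants demographics and history "presented in tabular form for all subjects enrolled in this study". Section 6.0 has device- or procedure-related adverse events and all serious adverse events recorded, and 6.2.2 has every SAE reported to the sponsor within 24 hours.

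**The concern.** Technical Success asks whether the device can resect the lesion without another modality. Getting the catheter into cutting position is part of that. If eligibility can be settled after the attempt has begun, the person who sees the device fail to reach a workable position also decides whether the subject counts. In a single-arm study meant to show that resections are safe and effective, there is no control group in which the same exclusion would operate.

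Safety is exposed in the same way. Under 5.7 the subject may already have been sedated, and the lesion injected and tattooed, when the attempt stops. A site then has one instruction to collect nothing and others to record and report.

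**Working it through.** **1. Order of events.** Consent and enrollment come first (5.3), with baseline in the 14 days before the procedure (5.6). At the index procedure (5.7) the subject is prepared and sedated, the lesion is found with the colonoscope, the device is set up, the lesion is injected and marked, and the catheter is advanced into cutting position. Nothing in 5.3 or 4.3 closes the screen-failure rule at any of these steps.

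**2. Where each kind of subject ends up.** ITT needs the EndoRotor to have been used for some resection (8.2). PP is the part of ITT with complete EndoRotor-alone resection (8.2). Safety is drawn from ITT (8.5).

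| Situation at index | Status under 5.3 | ITT | PP | Safety (8.5) |
|---|---|---|---|---|
| Lesion not reached with the colonoscope | Screen failure, no data | No | No | No |
| Catheter introduced, cannot be positioned, no resection attempted | Not clearly classified; can be read as screen failure | No | No | No |
| Same, then converted to another modality | Same | No | No | No |
| Inserted, resection attempted, no tissue removed | Safety follow-up to discharge, then exit | No | No | No |
| Some EndoRotor resection, then converted | In study | Yes | No | Yes |
| Resected with EndoRotor, later found ineligible | Stays in study, deviation filed | Yes | No | Yes |

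The second and third rows are the gap. The aborted-procedure sentence needs an attempted resection, and the later-found-ineligible rule needs treatment, so neither covers these subjects. For Safety, the 8.2 wording (treated with the device) could be read more widely than 8.5, but treatment is not defined there.

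**3. The no-data rule against the rest of the plan.** For one consented subject called a screen failure, 5.3 says "no data will be collected on these subjects". Section 5.1 requires a logged reason, 5.6 a recorded baseline and 8.1 a place in the demographics table. Sections 6.0 and 6.2.2 require related events and SAEs to be recorded or reported. These cannot all be followed.

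**4. Size.** The plan's only precision figure is in 8.8: n = 60, success rate 0.85, half width 0.0972. With x = 0.85 × 60 = 51, the Clopper-Pearson limits are the 0.025 quantile of Beta(51, 10) = 0.7343 and the 0.975 quantile of Beta(52, 9) = 0.9290. The half width is (0.9290 − 0.7343)/2 = 0.0974, which matches the stated value to within 0.0002. (The limits printed in 8.8, 0.782 and 0.967, do not reproduce. That is a separate matter, and nothing here depends on it.)

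The documents give no number of access or positioning failures. As an illustration only, suppose 51 of 60 subjects with some EndoRotor resection succeed, and k further subjects had the catheter introduced but not positioned. Counting those k as failures gives 51/(60 + k):

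| k (assumed) | Rate | 95% exact limits | Half width |
|---|---|---|---|
| 0 | 51/60 = 85.0% | 0.7343 to 0.9290 | 0.0974 |
| 1 | 51/61 = 83.6% | 0.7191 to 0.9185 | 0.0997 |
| 2 | 51/62 = 82.3% | 0.7047 to 0.9080 | 0.1016 |
| 3 | 51/63 = 81.0% | 0.6909 to 0.8975 | 0.1033 |
| 6 | 51/66 = 77.3% | 0.6530 to 0.8669 | 0.1069 |
| 10 | 51/70 = 72.9% | 0.6090 to 0.8280 | 0.1095 |

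Under this construction the 0.10 precision goal is missed from k = 2. The table shows sensitivity and does not estimate the bias.

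**The case against.** The strongest reply is that 8.2 and 8.5 would leave these subjects out of every set even if the 5.3 sentence were deleted. That is right: 5.3 is only part of the cause, and a change confined to 5.3 would not bring them back.

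It also rules out a tempting calculation. A reader might start from 9 failures in 60 and remove 3 or 6 of them, giving 51/57 = 89.5% or 51/54 = 94.4%. Neither is a denominator in this plan. Subjects with no EndoRotor resection never enter ITT, PP already excludes every incomplete resection, and recruitment runs to 60 evaluable subjects (3.1.2, 5.4).

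Three further inferences go beyond the text:

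- **Access problems usually surface only at the index colonoscopy.** The documents do not say so. The lesions are recurrent, 5.1 reviews previous examinations, 5.3 asks for eligibility to be ensured beforehand, and Appendix 1 marks a baseline endoscopy. Discovery at the index procedure is possible; its frequency is unknown.
- **Nothing is kept and harms go unrecorded.** The 5.1 log entry remains, resection-attempted aborts have safety follow-up to discharge, device malfunctions go on the CRF (6.2.3), and SAEs are reportable (6.2.2). The accurate statement is that the instructions conflict.
- **Every failure to reach the lesion is a device failure.** Section 5.7 limits the protocol to removal once the abnormal area has been identified with the colonoscope. Failure of the colonoscope to reach the lesion need not count against the EndoRotor.

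The study is also mainly descriptive (8.0), which lowers the stakes. It does not remove the point, because a descriptive success rate still needs a denominator that is not settled after the attempt.

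**Conclusion.** The point holds in this form. Section 5.3 allows an enrolled subject to be reclassified as ineligible after the index procedure has started. Together with 8.2 and 8.5, it leaves a subject in whom the EndoRotor could not be positioned outside ITT, PP and, on the 8.5 wording, Safety. Moving the primary analysis from PP to ITT would not recover such subjects. The no-data rule contradicts 5.1, 5.6, 6.0, 6.2.2 and 8.1 whatever view is taken of bias.

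The direction is toward a more favourable technical success and safety result. The size is unknown. The conclusion rests on reading any resection in 8.2 as actual removal of tissue, and on the absence of a time limit in 5.3 and 4.3. It does not assume that sites would misuse the rule.

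**What to change.** 1. In 5.3, make screen failure a status that is settled and entered on the CRF before the index procedure begins. Define that start so that sedation falls after it. Delete the no-data statement.
2. From that start, record the reason for stopping and all adverse events for every subject, including those whose lesion is not reached with the colonoscope and those sedated or injected but with no catheter introduced. Report these two groups separately, without counting them as device failures.
3. In 8.2 and 8.5, add an all-attempted set: every subject in whom the EndoRotor catheter was introduced into the endoscope. In that set, count inability to position or resect as a Technical Success failure. Base the safety set on it, and state how the 90-day safety result treats aborted cases that exit at discharge.
4. Reconcile 5.3 with 5.1, 5.6, 6.0, 6.2.2 and 8.1.

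A cut-off placed at catheter entry would not be enough by itself, because harms from sedation or injection before that moment would still have no clear collection route.

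The cost is protocol wording, one CRF field and one more analysis set. The reported success rate may be less favourable.

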5.4 Anticipated Total Enrollment

It is anticipated that sixty (60) evaluable patients will be enrolled. Loss to follow-up is anticipated to be no more than 10%.

5.5 Schedule of Events

A summary schedule of the study assessments is provided in **Appendix 1**.

5.6 Baseline Evaluation, not greater than 14 days prior to the Index Procedure

Baseline data will be collected after the subject signs the informed consent form in order to confirm **all** inclusion and **no** exclusion criteria are met. All assessments must be completed within the 14 days prior to undergoing the study procedure, with the exception of the pregnancy test. A negative pregnancy test within 1 day before the study procedure is required for women of childbearing potential.

The following baseline evaluations will be assessed and recorded on all patients who provide written informed consent:

- Demographic information
- Medical and surgical history, including risk factors
- Pregnancy test results (completed within 1 day before the study procedure)
- Physical examination
 - Vital signs
 - Height and weight
 - o Target review of symptoms
- Assessment against I/E criteria

5.6.1 Baseline Demographics and Relevant Medical History

The subject's demographic information and relevant medical history will be documented in the subject's source medical record and on the appropriate case report form (CRF). This will include the subject's:

- Age
- Gender
- Height
- Weight
- Race and Ethnicity Information

- Relevant medical history
- Physical Examination

5.7 Index Procedure

All patients will receive the EndoRotor® treatment following the technique described by Interscope's Instructions for Use.

The mucosal resections are performed during standard flexible colonoscopy procedures. All medications given, pre- and post-procedure precautions and follow-up assessments are part of routine standard of care. This protocol concerns itself with the actual removal of the mucosal lesion once the abnormal area is identified using the colonoscope.

- Patients will be prepped in the usual manner for lower GI endoscopy prior to their interventional visit.
- The procedures will be performed with either Propofol sedation or under general anesthesia.
- When a mucosal lesion is found, the EndoRotor® system will be prepared by attaching the EndoRotor® catheter, foot pedal and the calibrated suction to the Control Unit, ensuring there is a filter in the collection unit (specimen trap), and then priming the catheter with 0.9% normal saline.
- Lesions will be injected using saline solution with dye such as Indigo carmine or Methylene Blue. Indelible ink (such as SPOT) will be injected into the region of the resection to identify the site after resection.
- The EndoRotor® catheter will be inserted through the working channel of the endoscope until it is in proper cutting position with the cutting surface oriented towards the mucosal lesion and the catheter no more than 3cm out of the scope. The physician will turn the motor on by depressing the blue pedal and engage cutting by holding the orange pedal for as long as he/she wishes to cut tissue.
- Cutting should be performed while moving the EndoRotor® catheter. The endoscopist will take care to not keep the suction activated when he/she is not intending to cut mucosa and when stopped for more than 1 second while apposed to tissue to not risk creating a perforation.
- Various techniques can be used to remove the lesion. Recurrent, flat or sessile lesions will be attempted to be removed entirely with the EndoRotor® with no other treatment modalities. The physician will utilize the recommended technique appropriate to the lesion until there is no longer visible evidence of mucosal lesion. The intent of the protocol is to complete lesion resection using the EndoRotor as the only treatment modality. However, should it prove not feasible to complete the resection with the EndoRotor, the investigator may convert to the use of an alternative resection modality.

- For synchronous lesion interventions, respective lesion specimens should be isolated and separately collected to avoid confounding results.
- APC or similar techniques used for hemostasis on a resected lesion is not considered an alternative resection modality.
- Treat with EndoRotor, assess percentage of tissue removed with EndoRotor followed by photograph from region at equidistant location.
- Photo-document the region following EndoRotor treatment.
- If the complete lesion cannot be removed in a single treatment visit, a second visit can be scheduled to complete the removal in advance of the 90 day visit.

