1.3 Literature Summary

1.3.1 Rectum/Colon Polyps

Although most colon polyps are small (90% are less than 1cm) and never progress to cancer^(1,2), the larger polyps have a higher chance of harboring advanced histology and even cancer. Larger polyps and sessile polyps present the endoscopist with technical challenges in their resection that current instrumentation is not well-suited to address. EMR and Endoscopic Submucosal Dissection (ESD) are the main advanced techniques used to remove larger lesions by interventional endoscopists. When comparing the two, there are some striking differences between them. EMR involves the piecemeal resection of the lesion and is relatively quick depending on the endoscopist's skill and the size of the lesion. EMR is more widespread and is easier to learn (30-40 cases) than ESD that requires from 60 to 80 cases to become proficient. ESD requires the lifting of the lesion with fluid and the excision of the lesion in one piece. This meticulous resection requires much more time (45 to 90 minutes) but offers a surgical specimen that can be oriented and evaluated for margins and depth of penetration as one complete sample. ESD is much more commonly performed in Eastern Asia (Japan) than in Europe or the United States.

O'Brien, Michael J, et. al. reported results of an analysis encompassing 8401 person-years of follow-up evaluation⁽³⁾. AT and AR measures of adenoma flatness were 95% concordant. By the AT measure, flat adenomas (n 474) represented 27% of all baseline adenomas. Flat adenomas identified in the National Polyp Study cohort at baseline were not associated with a higher risk for high-grade dysplasia initially, or for advanced adenomas at surveillance. Flat adenomas were found to be no more likely to exhibit high-grade dysplasia than sessile (polypoid) or pedunculated adenomas.

At the present time, there are 2clinical literature reports specific to the EndoRotor® System dealing with recurrent adenoma in a single center and Barret's esophagus respectively. Based on clinical and extensive pre-clinical \results in a post-market setting, the EndoRotor® has several inherent advantages over EMR and ESD techniques in the removal of scarred lesions. It is cost-

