1.3.2 Summary

Following a review of the published literature, the main complications found to be associated with polypectomy were bleeding/hemorrhage, perforation, and post-polypectomy syndrome, which are reported to occur in 0-10.8%, 0-2.3%, and 0.14-3.7% of patients, respectively. Deaths were reported in only 2 studies, at a rate of 0.01% and 0.1%. The greatest risk factor for an adverse event is associated with increasing polyp size. In terms of performing polypectomy, the most commonly referenced outcome measures were completeness of polyp removal or recurrence, with a range from 73-100% and 1.4-24% respectively, in the published literature. Supporting evidence of a 3-month follow up visit, as is indicated in the EndoRotor colon study, was also reported in the medical literature. Additionally, it was determined that flat adenomas are no more likely to exhibit high-grade dysplasia than sessile (polypoid) or pedunculated adenomas thereby persistent and large adenomas would demonstrate the greatest potential for persistence as supported by the literature on incomplete resection rates, and therefore provides the rationale for the inclusion criteria in the EndoRotor colon study.

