5.7.1 Index Procedure Details

Refer to the Instructions for Use for a description of the procedure. The following data will be collected on all subjects during the index procedure and prior to discharge on the Index Procedure case report form:

- Summary of symptoms from physical examination
- Endoscopic imaging study
- The EndoRotor® achieved the attempted resection of the targeted lesion(s).
- The EndoRotor® pathological specimens were able to be interpreted by GI pathologists and enabled the rendering of clinical diagnoses.
- The total number of recurrent lesions treated with the EndoRotor.
- Time from scope insertion to scope removal.
- EndoRotor time from resection start to resection end.
- Adverse event assessment and treatment (i.e. delayed bleeding, presence of perforations). Note: Typical and routine steps (endoscopic clipping/mucosal apposition) will be taken to close perforations if they are discovered.
- Ease of use and overall satisfaction with the EndoRotor® System.
- Identification of technical difficulties and device malfunction, if any.
- Photographs post-EndoRotor treatment.

Current standard of care does not guarantee pathology in recurrent lesion procedures due to the difficulty to remove they often are treated with avulsion or Argon Plasma Coagulation. Since the EndoRotor retrieves specimen it can be sent for histopathological review. Although the EndoRotor is not intended for biopsy in this study pathologist will also be able to evaluate specimen that would normally be ablated. Resected tissue collected in the Specimen Trap will be placed in 10% Formalin and sent to the resident pathologist for histological evaluation. The

following steps will be taken for the review and interpretation of the specimens from the Specimen Trap following the procedure:

- 1. The resident pathologist shall be responsible for the preparation of the histology slides and the review and interpretation of the slides per hospital standard operating procedures.
- 2. The prepared specimen will be de-identified per hospital procedure and shipped by courier to an independent pathologist.
- 3. An independent pathologist selected by the Sponsor will prepare histology slides to assess the quality of the specimens.
- 4. The independent pathologist will document his/her assessment of the quality of the specimens.

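### No pre-treatment image or per-lesion size is required, so the reference for percentage completeness is neither guaranteed nor standardised, and outcomes cannot be described by lesion size from the listed data

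*Combined protocol and SAP*

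**What the plan says.** Section 4.2 defines secondary endpoint 1 as "Completeness, in percentage, of resection based on endoscopy film and/or photographs in addition to diagnostic assessment of specimen by the independent pathologist".

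Section 5.7 tells the operator to treat, then "assess percentage of tissue removed with EndoRotor followed by photograph from region at equidistant location", and in the next bullet "Photo-document the region following EndoRotor treatment". The index CRF list in 5.7.1 has "Photographs post-EndoRotor treatment" and, as a separate item, "Endoscopic imaging study", with no content or timing given for the latter.

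The lists in 5.6, 5.6.1 and 5.7.1 include demographics, history, a check against the eligibility criteria, a count of treated lesions and two procedure times. They do not include lesion size. Size appears as a 6 cm ceiling in the eligibility criteria (4.3) and in the description of the primary analysis (8.4). Section 1.3.2 states: "The greatest risk factor for an adverse event is associated with increasing polyp size".

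Section 8.4 places the secondary endpoints on the Per Protocol population. Section 8.2 restricts that population to subjects whose lesion was fully resected with the device alone.

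**The concern.** A percentage removed is a ratio, and its denominator is the lesion as it was before cutting began. If a site follows the written instructions and does no more, the images it must supply show only the treated region. A later reader then has no required view against which to judge how much was there.

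The absence of a size field raises a second problem. Small remnants and lesions near the 6 cm ceiling are pooled, and the listed data do not allow the report to say which were treated. A reader comparing these results with those of another device could not tell whether a good rate reflects the device or an easy mix of lesions. A view not captured before resection cannot be recovered afterwards.

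**Working it through.** The plan gives no figure for this endpoint, so there is nothing to reproduce. The check sets the sections side by side.

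1. **What the endpoint needs.** Completeness (%) = 100 × (extent before − extent remaining) / extent before. The extent before treatment enters both numerator and denominator.

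2. **Images explicitly required.** Two bullets in 5.7 and one item in 5.7.1 ask for photographs. After treatment: 3 of 3. Before treatment: 0 of 3. The word equidistant in 5.7 suggests a comparison view, but none is named.

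3. **Other possible sources of the reference.**
   - The imaging item in 5.7.1 may cover the view before treatment, but its timing is not stated.
   - Film is allowed by 4.2, as an alternative to photographs.
   - Appendix 1 marks endoscopy at baseline and at the procedure, footnoted as standard of care. It requires no image capture or measurement.
   - Table 2 (9.7.4) requires upload of procedure images without saying whether they precede or follow treatment.
   - The operator judges the percentage live under 5.7, having seen the lesion. However, 5.7.1 lists no field for that percentage. The nearest item is whether the device managed the intended resection.

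   Each may supply the reference; none is required to.

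4. **The specimen.** Section 1.1 describes roughly 1,750 cuts a minute, with tissue aspirated onto a filter. Under 5.7.1 the independent pathologist documents specimen quality. The protocol credits a different technique, one-piece submucosal dissection, with a method that "offers a surgical specimen that can be oriented and evaluated for margins and depth of penetration as one complete sample" (1.3.1). Nothing in the plan says the filtered tissue will yield the lesion's original extent.

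5. **Size and related descriptors.** Size is not among the items in 5.6, 5.6.1 or 5.7.1; nor are lesion location and scarred base. Prior resection could fall under medical and surgical history. The eligibility check in 5.6 confirms that a lesion is within 6 cm but does not ask for its measurement. Section 8.4 expects documentation up to that limit and names no field.

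6. **Where the endpoint is reported.** Per Protocol membership already requires complete resection with the device alone. Completeness in that set is therefore close to 100% by construction, provided the same judgement of completeness is used for both. Partial resections fall in the Intent to Treat set, where 8.4 does not place this endpoint.

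7. **Related quantities.** Section 5.8 asks for a percentage of tissue persistence at 90 days, also without a stated denominator. Section 5.7 permits a second visit to finish the removal, in which case cumulative completeness refers back to the lesion before the first visit.

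8. **What a table by size could support.** As an assumption, take the upper ends of the polypectomy ranges in 1.3.2 and 60 subjects. Bleeding: 60 × 0.108 = 6.5 expected. Perforation: 60 × 0.023 = 1.4 expected. These counts allow description by size, not inference.

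**The case against.** The strongest reply is that the reference probably exists in practice. Endoscopy takes place at baseline and at the procedure, images are uploaded, and the operator estimates the percentage while looking at the site. The CRFs themselves are not in the documents, so the list in 5.7.1 may not be the whole form. Measured size may sit in source records, against which monitors verify the eCRFs (10.3). In addition, the planned Per Protocol summary of completeness would hardly move whether or not an earlier image existed.

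Much of this stands, and it rules out three stronger readings that a reader might infer.

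- That completeness cannot be derived at all. The sources in step 3 may permit it; what is missing is a requirement.
- That the figure rests on the operator's memory. Section 5.7 describes an assessment made during the procedure.
- That the 6 cm limit cannot be checked. Eligibility is recorded, and the limit can be verified in source.

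A reader might also want to size the problem by the range of lesion areas that 6 cm allows. The documents give no size distribution, and a per-lesion percentage is already relative to that lesion, so such a figure would not measure the harm.

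What the reply does not answer is that none of these sources is required, matched in view or linked to a listed field. The Per Protocol argument shows that completeness is being reported where it can tell least; it does not show that the reference is unnecessary.

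**Conclusion.** The point holds as a gap in what the plan requires to be collected. The only photographs it explicitly asks for are taken after treatment, and no listed item records lesion size. The reference for percentage completeness is therefore left to local practice, and outcomes cannot be described by lesion size from the listed data.

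The consequence is moderate. It affects one descriptive secondary endpoint, the 90-day persistence percentage and the description of case mix. It changes neither the definition of Technical Success nor any figure in 8.8. The conclusion assumes that the lists in 5.6, 5.6.1 and 5.7.1 reflect the CRFs; if the forms already hold a size field and an image taken before treatment, only the protocol text needs to catch up.

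The plan does not need a redesigned endpoint. A reader might infer that the specimen assessment should move from endpoint 1 to endpoint 4, but nothing here requires that.

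**What to change.** - In 5.7 and 5.7.1, require one still of each target lesion before treatment, at the same distance as the one taken afterwards.
- On the Index Procedure CRF, add for each lesion its longest diameter, location, prior resection and scarred base (yes/no). Add also the operator's percentage removed, defined relative to the extent before treatment.
- In 8.4 and 8.6, report completeness on the Intent to Treat set of 8.2 as well as Per Protocol.
- Add a descriptive table of Technical Success, persistence and SAEs by lesion size, labelled as not for inference at about 60 subjects.

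The cost is one extra image per lesion and slightly more data entry during a colonoscopy that is already taking place. No visit or procedure is added, and the sample size is unchanged. The image pair makes the operator's percentage checkable, but it does not by itself provide an independent reading.
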